In the MEADs trials, the most commonly reported AEs following treatment with Ozurdex are those frequently observed with ophthalmic steroid treatment or intravitreal injections: cataract formation, elevated intra-ocular pressure (IOP), and conjunctival or vitreal hemorrhage. In these trials, cataract-related AEs were observed in 67.9% of patients with a phakic eye at baseline compared to 20.4% of patients in the sham group. The incidence of cataract-related AEs increased after the first year after Ozurdex injection. Approximately one-third of patients with Ozurdex implant had a clinically significant increase in IOP requiring treatment during the study. Vitreous hemorrhage considered possibly related to treatment was reported in 3.5% of patients with Ozurdex implant compared to 0.0% in the sham group. Less frequently reported but more serious adverse drug reactions include endophthalmitis, necrotizing retinitis, retinal detachment and retinal tear. With the exception of headache and migraine, no systemic adverse drug reactions were identified with the use of Ozurdex. Finally, several adverse drug reactions, such as conjunctival hemorrhage, visual acuity reduced, vitreous detachment, vitreous floaters, vitreous opacities, eye pain, photopsia, conjunctival edema, conjunctival hyperemia, endophthalmitis, retinal detachment, retinal tear, hypotony of the eye, anterior chamber inflammation, anterior chamber cells/flare, abnormal sensation in eye, scleral hyperemia, device dislocation, and complication of device insertion, have been identified in Ozurdex SmPC as related to the intravitreal injection procedure, i.e. the frequency of these AEs is proportional to the number of treatments given.

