#### 8.2.1 Inclusion Criteria

A patient must meet **all** of the following criteria to be eligible for participation in the study.

1. Patient received at least two Ozurdex implants in the study eye to treat visual impairment due to DME
2. Male or female patient aged  $\geq 18$  years at time of first Ozurdex implant injection
3. First Ozurdex implant injection occurred after 1 January 2015
4. Patient was followed-up at the site for at least 12 months after the first Ozurdex implant in the study eye

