### Study design

[figure not shown]
Study CMO-MA-EYE-0564 is a retrospective, non-interventional, observational, multi-center, drug utilization study to be conducted in adult patients with visual impairment due to DME treated with Ozurdex implants in Germany and Switzerland from 1 January 2015 to 1 September 2018. Data from approximately 150 patients will be collected by retrospective review of medical charts; including up to 50 patients that are naïve of any anti-VEGF treatment before their first Ozurdex implant injection. Sites will be hospital-based experienced medical retina centers treating DME patients.

[figure not shown]
Patients' medical charts will be selected over a 4-month period at each site or until the study target population has been reached. Site personnel will be invited to complete a screening log with all patients who received their first Ozurdex implant injection from 1 January 2015 until 1 September 2017 to help them identify eligible patients. For each patient, retrospective data on the study eye will be abstracted from existing medical records from time of first Ozurdex implant injection until 1 September 2018. Data abstraction will cover at least one year of follow-up after first Ozurdex injection for all selected patients. The study eye will be defined as the eye that received the most Ozurdex injections. Key relevant data will also be collected on the contralateral eye.

Consent from patients will not be requested; as the study is retrospective and anonymized, a waiver of consent will have been requested from the Ethics Committees.

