### Sites and study population

Site selection will aim to recruit qualified ophthalmologists experienced in intravitreal injections who are most likely to treat patients with DME with Ozurdex. A sample of ophthalmologists working in experienced medical retinal centers treating DME patients will thereby be selected.

From a public health and market access perspective, the present study population constitutes a broader real-world patient population than that reflected in clinical trials. The present study design cannot make any conclusions on causal relationships, but can rather explore real-world Ozurdex drug utilization patterns, effectiveness and safety. It is expected that the results from this study may be generalizable to the overall population presenting with DME and treated with Ozurdex in Germany and Switzerland.

Patients may contribute at most one eye into the study. If both eyes meet the inclusion and exclusion criteria, the eye that received the most Ozurdex injections will be chosen as the study eye.

Inclusion criteria are:

1. Patient received at least two Ozurdex implants in the study eye to treat visual impairment due to DME

2. Male or female patient aged  $\geq 18$  years at time of first Ozurdex implant injection in the study eye
3. First Ozurdex implant injection in the study eye occurred after 1 January 2015
4. Patient was followed-up at the site for at least 12 months after the first Ozurdex implant injection in the study eye

Exclusion criterion is:

1. Patient received Ozurdex implants in the study eye as part or during a clinical study

[REDACTED]

[REDACTED]

[REDACTED]

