### 15.2.4 Fourth Secondary Objective

The secondary objective '*To present those AESIs that may be potentially related to Ozurdex reinjection*' will be assessed by the presence of the following AESIs:

- Cataract or lens opacities
- Glaucoma
- Hypotony
- Implant dislocation
- Infection vs. Non-infection related ocular inflammation
- Intraocular hypertension
- Mechanical failure of device and implant misplacement
- Ocular bleeding or hemorrhage
- Retinal detachment (tear or hole)
- Significant vitreous loss
- Vitreous detachment

These AESIs will be identified from eCRF section '*Adverse events*' (AE/F20 form) in which they are pre-listed.

All AESIs that began on or after the date of the first Ozurdex injection in the study eye will be considered for analysis. The analysis will be performed:

- considering all AESIs, AESIs that occur in the study eye, and AESIs that occur in the contralateral eye.
- cumulatively considering all AESIs and broken down by the number of injections, i.e. considering AESIs that occur after the first Ozurdex injection at baseline, AESIs that occur after the first Ozurdex reinjection, AESIs that occur after the second Ozurdex reinjection, etc. AESIs that occur on the same day of an Ozurdex injection will be considered as occurring after the injection.

AESIs will be summarized using descriptive statistics for the following parameters:

- Number and percentage (with 95% CI) of patients who experienced at least one AESI.

[REDACTED]

[REDACTED]

[REDACTED]

[REDACTED]

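### AESI percentages by injection number (SAP 15.2.4) rest on unequal time at risk, so for events that accrue over time the rows cannot be compared

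*SAP*

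**What the plan says.** SAP 15.2.4 takes all AESIs that start on or after the first injection and analyses them "cumulatively considering all AESIs and broken down by the number of injections, i.e. considering AESIs that occur after the first Ozurdex injection at baseline", then after the first reinjection, the second, and so on. The visible summary is "Number and percentage (with 95% CI) of patients who experienced at least one AESI"; four items after it are redacted. SAP 16.0 refers the whole safety analysis to this section.

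The following parts of the plan determine how long each row is observed:

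- Eligibility (SAP 4.0): "Patient received at least two Ozurdex implants in the study eye to treat visual impairment due to DME" and "Patient was followed-up at the site for at least 12 months after the first Ozurdex implant injection in the study eye".
- Screening log (SAP 4.0): "all patients who received their first Ozurdex implant injection from 1 January 2015 until 1 September 2017".
- Data collection (SAP 4.0): "retrospective data on the study eye will be abstracted from existing medical records from time of first Ozurdex implant injection until 1 September 2018".
- SAP 21.2 ends the follow-up period at the last study visit or the first concomitant anti-VEGF or corticosteroid, whichever is earlier. SAP 15.2.4 does not say whether this applies to AESIs.
- SAP 21.3.4 derives AESI duration and the time from the last injection on or before onset. SAP 21.3 says it covers all derived variables, and no time at risk per injection is among those visible.

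**The concern.** A percentage of patients with an event depends on how long they were watched. Here that length differs by row for reasons unrelated to risk. The period after injection 1 is normally closed by the second implant that eligibility requires. The period after a patient's last implant goes on until observation ends. Any patient who stops Ozurdex but stays under follow-up therefore adds a long period to a reinjection row and never to the first row.

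This matters most for AESIs that build up with time: cataract, intraocular hypertension and glaucoma. Protocol 5.1 itself notes that "The incidence of cataract-related AEs increased after the first year after Ozurdex injection". The objective is about events potentially related to reinjection, so the table invites a comparison between rows. Protocol 7.3.3 and SAP 7.0 also foresee comparing safety events with the literature. SAP 15.1 deals with unequal follow-up for reinjection counts by using complete-year denominators in Years 2 and 3. The visible text of 15.2.4 has no counterpart.

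**Working it through.** **1. The plan's own figure.** The only sizing for the full sample is the half-width 1.96 × SD/√150. For SD 1.5, 2.0, 2.5 and 3.0 months this is 0.24, 0.32, 0.40 and 0.48, which agrees with the stated 0.2 to 0.5 months. No figure is given for AESIs.

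**2. Inputs from the documents.** Potential follow-up runs from 12 months (1 September 2017 to 1 September 2018) to 44 months (1 January 2015 to 1 September 2018). Planning values for the interval are means of 4.7 to 6.7 months and SDs of 1.5 to 3.0 months.

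**3. Assumptions not in the documents.** These are a constant AESI hazard h, identical after every injection; follow-up uniform over 12 to 44 months; and the share of patients who stop at each step after the second implant. On stopping, the nearest figure is the 66% who received a second implant within a year in a cited one-year study (Protocol 5.1).

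**4. Closed form, patient with exactly two implants.** P(event in t months) = 1 − exp(−h·t), with h = 0.02 per month.

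- First interval 4.7, follow-up 24 months: 1 − exp(−0.094) = 9.0% against 1 − exp(−0.386) = 32.0%; ratio 3.6.
- First interval 6.7, follow-up 44 months: 12.5% against 1 − exp(−0.746) = 52.6%; ratio 4.2.
- First interval 6.7, follow-up 12 months: 12.5% against 1 − exp(−0.106) = 10.1%; ratio 0.80.

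**5. Cohort simulation** (second implant guaranteed, follow-up 12 to 44 months, denominator = patients who received that injection). Setting A: lognormal intervals, mean 5.0, SD 1.8 months, h = 0.3 per year. Setting B: gamma intervals, mean 6.0, SD 2.5 months, h = 0.02 per month.

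| Stop at each step | A: after injection 1 vs reinjection 1 | Ratio | B: after injection 1 vs reinjection 1 | Ratio |
|---|---|---|---|---|
| 0% | 11.7% vs 11.6% | 1.0 | 11.2% vs 11.0% | 0.99 |
| 10% | 11.7% vs 14.7% | 1.26 | 11.2% vs 13.4% | 1.20 |
| 20% (A), 25% (B) | 11.7% vs 17.8% | 1.5 | 11.2% vs 16.9% | 1.51 |
| 50% | 11.7% vs 26.8% | 2.3 | 11.2% vs 22.7% | 2.03 |

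In A with 50% stopping, mean time at risk is 5.0 months after injection 1 and 14.0 months after reinjection 1. With every patient followed for exactly 12 months and 0% to 50% stopping, the ratio is about 0.93 to 1.16 in A and 0.82 to 0.94 in B.

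**6. Denominator.** With all patients as denominator, A with 50% stopping gives 11.6%, 26.9%, 11.4% and 4.5% after injections 1 to 4. The later rows fall below the first although the hazard never changes.

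**7. End-of-follow-up rule.** Applying SAP 21.2 with an assumed switch rate of 0.02 per month lowers the ratio in B at 25% stopping from 1.51 to 1.41.

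**8. Behaviour of possible remedies.**

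- Events per 100 patient-years, B at 25% stopping: 24.0, 24.3, 23.9 and 23.7 after injections 1 to 4 (true value 24.0). The artefact disappears.
- The same rate misleads for procedural events. With a constant 2% risk per injection in A at 50% stopping, it is 0.02/(5.0/12) = 4.8 per 100 eye-years after injection 1 against 0.02/(14.0/12) = 1.7 after reinjection 1.
- Kaplan-Meier at 6 months, censored at the next injection, A at 50% stopping: 13.9% against 14.0%. The true value is 1 − exp(−0.3 × 0.5) = 13.9%.
- A 6-month percentage limited to intervals observed in full or containing an event: about 34% against 19%. This is biased, because event-free intervals that end early are dropped.

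**9. Cumulative percentage.** Take the 67.9% cataract figure for phakic eyes in the 3-year trials (Protocol 5.1). A constant hazard gives −ln(1 − 0.679)/3 = 0.379 per year, hence 31.5% at 12 months and 56.9% averaged over follow-up uniform on 1 to 3.67 years. This only illustrates the dependence on follow-up: the protocol reports a rising incidence, which a constant hazard does not reproduce.

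**The case against.** The strongest objection concerns direction. A reader might infer that reinjection is bound to look riskier. The documents do not support that. The effect needs patients who stop well before follow-up ends, and no stopping rate is given. Without stopping the ratio is about 1, and with follow-up near 12 months it can fall below 1. Against this, Protocol 9.2 selects patients from the earliest first injection onward, which favours long follow-up and makes the upward case plausible, though not certain.

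A reader might also infer that the last period is open-ended. It is not: it stops at the last visit, with data to 1 September 2018, and perhaps earlier under SAP 21.2. If that rule governs AESIs, the first period can also end before the reinjection.

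Four items are redacted and could hold further measures, so nothing can be said beyond the visible text. The rows could also be read as nested (any time after injection j). The derivation in SAP 21.3.4 points to attribution to the last injection, and under nesting time at risk is still unequal.

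Finally, the study tests no hypothesis and disclaims causal conclusions, and for device and procedural events a percentage per injection is the natural measure. The last point stands and shapes the fix. The descriptive purpose limits the consequence but does not make the rows comparable.

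**Conclusion.** The concern holds in a limited form. In the visible text of SAP 15.2.4, percentages by injection number are not comparable for AESIs that accrue over time, and a reader cannot correct them because neither time at risk nor the denominator is given.

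Under a constant hazard, with follow-up of 12 to 44 months and 10% to 50% stopping at each step, the first reinjection shows about 1.2 to 2.3 times the percentage of the first injection in settings A and B. Over the plan's wider range of interval means and SDs, the spread is 1.14 to 2.77. If all continue or follow-up is near 12 months, the ratio is about 0.8 to 1.2. Stopping rates, hazards and the follow-up distribution are assumptions. Procedure- and device-related events are outside this conclusion.

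One further distortion is not quantified here. Patients who had an AESI after the first implant and for that reason were not reinjected are ineligible, which lowers the first row. No analysis of this sample can remove that, so it should be stated as a limitation.

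**What to change.** In SAP 15.2.4, for study-eye AESIs:

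- Attribute each event to the last injection on or before onset, as in 21.3.4. State the number of eyes at risk per injection, and whether the 21.2 end of follow-up applies.
- Report a Kaplan-Meier percentage with 95% CI within a common window after each injection (for example up to 6 months, the release period in Protocol 5.1), censored at the next injection or end of observation. Do not restrict to intervals observed for the full window or with an event.
- Add events per eye-year by injection interval for time-accruing AESIs only. Keep events per injection for procedure- and device-related AESIs.
- For the cumulative result, add Kaplan-Meier estimates at 12, 24 and 36 months.
- Keep the planned counts and percentages as supporting information.

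The cost is SAP wording and a few more table columns; the plan's existing derivations already use injection, AESI-onset and last-visit dates. Later reinjections will have wide CIs because few eyes reach them. Censoring at the next injection also assumes that the timing of reinjection is unrelated to AESI risk, which should be stated.

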### **12.2 BIOMICROSCOPY**

At baseline, the number and percentage of patients with biomicroscopy data available for the study eye will be described. Then, for patients with data available, the following parameters will be described:

- Any adverse findings (Yes, No)
- Conjunctiva (bulbar or palpebral): hyperemia (Normal, Trace +0.5, Mild +1, Moderate +2, Severe +3), edema (Normal, Trace +0.5, Mild +1, Moderate +2, Severe +3), subconjunctival hemorrhage (Normal, Trace +0.5, Mild +1, Moderate +2, Severe +3). Adverse findings will also be described as 'Absent vs. Present' [DV].
- Cornea: edema (Normal, Trace +0.5, Mild +1, Moderate +2, Severe +3), superficial punctate keratopathy (Normal, Trace +0.5, Mild +1, Moderate +2, Severe +3). Adverse findings will also be described as 'Absent vs. Present' [DV].

- Anterior chamber: cells (Normal, +0.5, +1, +2, +3, +4), flare (Normal, Faint +1, Moderate +2, Marked +3, Intense +4), hypopyon (Present, Absent) and, if present, level in mm. Findings on cells and flare will also be described as 'Absent vs. Present' [DV].
- Iris/Pupil: pathology (Present, Absent), peripheral iridotomy noted (Yes, No), rubeosis iridis (according to categories 'Normal, +0.5, +1, +2, +3'). Adverse findings will also be described as 'Absent vs. Present' [DV]. Pathologies will be described by PT (MedDRA version 21.1). If more than one pathology with the same PT have been reported for the same patient, s/he will be counted once for that PT.

During the follow-up period, the number and percentage of patients having at least one adverse finding in the study eye (Yes, No) [DV] will be described. Then, for all patients with at least one adverse finding, the type of adverse finding will be described as 'Present, absent' for each pre-listed category: conjunctiva (hyperemia, Edema, subconjunctival hemorrhage), cornea (edema, superficial punctate keratopathy), anterior chamber (cells, flare, hypopyon) and iris/pupil (pathology, peripheral iridotomy, rubeosis iridis). If an adverse finding has been reported more than once for the same category for the same patient, s/he will be counted once for that category. For patients with at least one adverse finding during the follow-up period, a listing will also be presented with all biomicroscopy results at baseline and during the follow-up period.

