## 12.4 IOP

IOP (mmHg) in the study eye will be summarized at baseline using descriptive statistics.

IOP (mmHg) measured at 7-12 weeks after the first Ozurdex injection in the study eye, as well as at 7-12 weeks after each reinjection in the study eye, will be described using descriptive statistics. A figure will be presented for the mean IOP (mmHg) with 95% CIs at baseline, at each Ozurdex reinjection, and at 7-12 weeks after each Ozurdex injection in the study eye. In addition, the change in IOP (mmHg) from baseline to 7-12 weeks following each Ozurdex injection [DV], and the change from each Ozurdex reinjection to 7-12 weeks following reinjection [DV] will be described using descriptive statistics.

The following rules will apply for this description:

- IOP assessed on or after the day of subsequent injections (injection 2, injection 3, etc) will be included in this description.
- If there is more than one IOP measurement within the 7-12 week time window, the mean value will be considered for the description (See rule defined in section 21.2).
- If an Ozurdex injection is performed in the study eye at a follow-up visit, then investigators are asked to report in the EDC the IOP measured before the injection. This value will be considered for analysis.

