### Time from the last Ozurdex injection (before or the day of AESI) to AESI

The time will be derived in days as:

Onset date of AESI – Date of the last Ozurdex injection. The last Ozurdex injection will be identified as the last injection among those performed on or before the onset date of the AESI.

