### **21.3.5 Variables Related to BCVA and CRT**

#### BCVA conversion

The method of assessment for BCVA can be reported in the EDC as ETDRS, Snellen (Feet), Snellen (Meters), or Snellen (Decimal). For analysis, all values will be converted into approximate ETDRS letters.

Snellen converted to approximate ETDRS letters =  $85 + [50 * \log(\text{Snellen fraction})]$

BCVA and CRT: Last assessment prior to each Ozurdex injection

For the first Ozurdex injection in the study eye, the last assessment prior to Ozurdex injection (= baseline assessment) is specifically requested in the eCRF. Therefore, the last assessment is directly available.

For subsequent Ozurdex injections in the study eye, the last assessment prior to the  $j^{\text{th}}$  injection ( $j \geq 2$ ) will be identified considering all assessments available between the day after the  $(j-1)^{\text{th}}$  injection to the day of the  $j^{\text{th}}$  injection included (i.e. date of  $(j-1)^{\text{th}}$  injection  $<$  Date of assessment  $\leq$  Date of  $j^{\text{th}}$  injection). The underlying assumption is that assessments performed at a visit at which an Ozurdex injection is performed are considered as performed before the injection.

BCVA and CRT: Change from baseline to 7-12 weeks following injection  $j$

For each injection  $j$  ( $j \geq 2$ ), the change will be calculated as:

Value at 7-12 weeks following injection  $j$  – Last value prior to the first (baseline) Ozurdex injection in the study eye. See Section 21.2 for the definition of the '7-12 weeks' time window and for the rule in case of multiple assessments within the time window.

BCVA and CRT: Change from the assessment prior to injection  $j$  to 7-12 weeks following injection  $j$

For each injection  $j$  ( $j \geq 1$ ), the change will be calculated as:

Value at 7-12 weeks following injection  $j$  – Last value prior to Ozurdex injection  $j$ . See Section 21.2 for the definition of the '7-12 weeks' time window and for the rule in case of multiple assessments within the time window.

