### **21.4 IMPUTATION OF MISSING DATA**

Partial date fields with missing day will be imputed as the first of the month. Partial date fields with missing day and month will be imputed as 01JUL.

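### AESIs dated on an injection day are all credited to the new implant, although the IOP entered at a reinjection visit is the pre-injection value

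*SAP*

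**What the plan says.** **AESI timing.** SAP 15.2.4 takes AESIs from the adverse event form of the eCRF, where they are pre-listed. On scope: "All AESIs that began on or after the date of the first Ozurdex injection in the study eye will be considered for analysis". It tabulates them cumulatively and by injection number. For ties it says: "AESIs that occur on the same day of an Ozurdex injection will be considered as occurring after the injection". No exception is made by type of event or by how the event was found. SAP 21.3.4 derives the time from the last injection to the AESI consistently with this: "The last Ozurdex injection will be identified as the last injection among those performed on or before the onset date of the AESI". A same-day event therefore gets 0 days.

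**Measurements on injection days.** For follow-up visits with an Ozurdex injection, SAP 12.4 says that "investigators are asked to report in the EDC the IOP measured before the injection", and that value is analysed. For BCVA and CRT, SAP 21.3.5 assumes that "assessments performed at a visit at which an Ozurdex injection is performed are considered as performed before the injection".

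**Other examinations.** Lens status, biomicroscopy and ophthalmoscopy (SAP 12.1 to 12.3) are summarised at baseline and over follow-up as a whole. No order relative to a same-day injection is stated for them.

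**First injection day.** SAP 21.2 defines baseline as the day of the first injection in the study eye and starts follow-up the day after.

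**AESI types.** Protocol 10.9.2 defines intraocular hypertension through IOP. Protocol 5.1 lists vitreous detachment among the reactions linked to the injection procedure.

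**The concern.** The fourth secondary objective presents AESIs potentially related to reinjection, and SAP 16.0 makes it the whole safety analysis. The by-injection breakdown is where a reader would look for a change in risk as implants accumulate.

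An injection visit can also be an examination visit. If raised pressure is found at the check before the injection, and the site enters that visit date as the onset, SAP 15.2.4 files the event under an implant that had not been given when the pressure was read. For events found before the injection the error runs one way only, towards the higher injection number, so it inflates the rows after reinjection. It also creates 0-day latencies that look like immediate effects of the new implant.

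The order of events cannot be recovered later. Protocol section 12 says that no queries will be issued, because investigators cannot link a record back to its patient.

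**Working it through.** The plan states no AESI rate and no share of AESIs dated on injection days, so it has no figure of its own to reproduce. The check sets the date rules side by side and then illustrates the size.

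**1. The rules for one injection day**

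| Item | Source | Placed relative to that day's injection |
|---|---|---|
| Any AESI with onset that day | SAP 15.2.4, 21.3.4 | After, 0 days |
| IOP at a follow-up injection visit | SAP 12.4 | Before |
| BCVA, CRT | SAP 21.3.5 | Before |
| Lens status, biomicroscopy, ophthalmoscopy | SAP 12.1 to 12.3 | Not stated |

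Intraocular hypertension is the clear case: it is defined by IOP, and the IOP entered is by instruction the pre-injection one. For glaucoma and cataract or lens opacity the same shift is possible, but the documents do not say whether the examination came first.

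**2. Condition for a wrong row.** Two things must both hold: the event was found before the injection, and its onset was entered as that day. The SAP works from onset, so an event with an earlier recorded onset already goes to the earlier implant. Imputation is a separate matter. Under SAP 21.4, "Partial date fields with missing day will be imputed as the first of the month"; this creates a same-day tie only if the injection fell on the first of that month.

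**3. Latency.** SAP 21.3.4 uses 1 month = 365.25 ÷ 12 = 30.4375 days. The planning means in SAP 19.0 run from 4.7 to 6.7 months.
- 4.7 × 30.4375 = 143 days
- 6.7 × 30.4375 = 204 days

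At those intervals, an event found at the pre-injection check was found 143 to 204 days after the preceding implant and is recorded at 0 days after the new one. Its true onset may lie anywhere between, so 143 to 204 days is an upper limit for the distortion.

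**4. By-injection percentages (illustration only).** Assumptions: 150 patients, all with a first reinjection (eligibility requires two implants); 30 with an AESI after the first injection and 30 after the first reinjection; a share s of the first-interval events found before, but dated on, the first reinjection day; different patients in the two rows. The rows become (30 − 30s)/150 and (30 + 30s)/150, with Clopper-Pearson 95% CIs as in SAP 21.1.

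| s | After first injection | After first reinjection |
|---|---|---|
| 0% | 30/150 = 20.0% (13.9 to 27.3) | 30/150 = 20.0% (13.9 to 27.3) |
| 10% | 27/150 = 18.0% (12.2 to 25.1) | 33/150 = 22.0% (15.7 to 29.5) |
| 30% | 21/150 = 14.0% (8.9 to 20.6) | 39/150 = 26.0% (19.2 to 33.8) |
| 50% | 15/150 = 10.0% (5.7 to 16.0) | 45/150 = 30.0% (22.8 to 38.0) |

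The events only change rows, so the cumulative percentage does not move.

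**5. Day 1.** SAP 15.2.4 includes onset on the first injection date, which SAP 21.2 calls baseline and places before follow-up. A finding made before the first implant, and also entered as an AESI dated that day, would add at most 1/150 = 0.7 percentage points per patient to the overall percentage. Five such patients, an assumed number, would add at most 5/150 = 3.3 points.

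**The case against.** The strongest reply is that events and measurements are different things. AESIs are not derived from IOP values; they come from their own form, and SAP 15.2.4 and 21.3.4 agree with each other. Counting same-day events as post-injection is a conservative safety convention. It is plainly right for implant misplacement, vitreous loss or a same-day haemorrhage. This stands, and it is why the rule should remain the main analysis.

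It is also true that nothing in the documents says sites date an AESI by the visit at which it was found. On Day 1, glaucoma and ocular hypertension have their own baseline fields (SAP 10.2), as do lens opacities (SAP 12.1). A condition that began earlier fails the test of onset on or after the first injection. Double entry is possible but not indicated. The study is descriptive, has no hypothesis (Protocol section 6) and disclaims causal conclusions (Protocol 8.2).

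Three stronger readings are tempting and are not supported:
- A reader might infer that every same-day examination counts as pre-injection, so that the SAP contradicts itself throughout. The convention covers BCVA, CRT and IOP only.
- A reader might infer that events will certainly be misplaced, or that the overall AESI percentage is inflated in general. The first depends on how onset was entered; the second could arise only through Day 1.
- A reader might move every AESI found by examination, vitreous detachment included, to the earlier implant. Protocol 5.1 ties vitreous detachment to the injection procedure, so that would separate it from its likely source.

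The convention does not cover the remaining case: a pressure event found on a reading that the SAP itself treats as taken before the injection.

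**Conclusion.** The point holds in a limited form. An intraocular hypertension AESI detected on the pre-injection reading and dated that day can be credited to the new implant with 0 days latency. Glaucoma and cataract or lens opacity may be affected in the same way, with less certainty because their same-day examinations have no stated order.

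For reinjections the effect is confined to the by-injection breakdown and the latency. For events found before the injection it always runs towards the higher injection number. The number of events is unknown; the percentages above rest on assumed counts and only show how far the rows could move. Parts of SAP 15.2.4 are blacked out, so further breakdowns by timing may exist that cannot be seen. A clarification and a sensitivity table are warranted; replacing the main rule is not.

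**What to change.** In SAP 15.2.4 and 21.3.4:

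1. Keep the same-day rule as the main analysis for all AESIs, and without change for procedure-related ones, including vitreous detachment.
2. In the by-injection table, show AESIs dated on an injection day as a separate row, with Day 1 shown apart. State that their 0-day latency is not to be read as time to onset.
3. Add a sensitivity table that assigns same-day intraocular hypertension, glaucoma and cataract or lens opacity to the preceding interval, or to baseline if dated Day 1. For study-eye intraocular hypertension, use the same-day pre-injection IOP where available. Protocol 10.9.2 gives no pressure threshold for this AESI, so the study team should either fix one before the analysis or list the readings beside the events. The SAP 12.4 instruction concerns follow-up visits; on Day 1 the baseline IOP is the value to use.

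The cost is a paragraph of SAP text and one extra table, from data already collected. The downside is that, in the sensitivity table only, a few true pressure rises later on the injection day would be credited to the earlier implant. The separate row shows the most events that could be involved.
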